7.7.1.3 Reporting Periods for Adverse Events and Serious Adverse Events

The safety reporting period for all AEs and SAEs is from study Day 1 (predose) through the EOT visit or 30 days after last study treatment (denintuzumab mafodotin or any component of RICE), whichever is later. However, all study protocol-related AEs are to be recorded from the time of informed consent. All SAEs that occur after the safety reporting period and are considered study treatment-related in the opinion of the investigator should also be reported to the sponsor.

SAEs will be followed until significant changes return to baseline, the event stabilizes (recovering/resolving) or is no longer considered clinically significant by the investigator, or the patient dies or withdraws consent. All non-serious AEs will be followed through the safety reporting period. Certain non-serious AEs of interest may be followed until resolution, return to baseline, or study closure.

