7.7.5 Ocular Monitoring Plan

In order to assess the effects of denintuzumab mafodotin on the eye, patients in both study arms will have complete ophthalmology assessments at protocol-defined timepoints (see Section 6 and [Appendix A](#)). Ophthalmology assessments are to include, but are not limited to, visual acuity and slit lamp examination. A baseline dilated fundus examination is required; subsequent dilated fundus examinations are to be conducted as clinically indicated. In particular, corneal epithelium changes must be assessed at each timepoint. Assessments must also include evaluation of steroid eye drop-induced changes including, but not limited to, intraocular pressure measurements and subcapsular cataracts. In addition, ophthalmologic evaluations will be obtained in the event of subjective visual or ocular disturbances while on study.

The results of the ophthalmological exam should be reviewed prior to the next dosing of denintuzumab mafodotin, and dose modifications of denintuzumab mafodotin should be made based on ocular toxicity grading of symptoms or corneal changes (see Section 5.8.1 and [Appendix E](#)) following discussion with the medical monitor.

Ophthalmology exams and ocular health surveys are required at baseline, the end of Cycles 2 and 3 (Days 15–21), EOT, and approximately 30-days post ASCT (for those patients who proceed to ASCT). In the event of ocular toxicity, ophthalmology exams should be conducted at least monthly during the follow-up period (unless discussed with the medical monitor) until resolution or return to baseline.

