7.6.1.1.1 Ocular AEs

Incidence, onset and improvement/resolution of ocular AEs of interest will be summarized based on the safety analysis set. The ocular AEs of interest will be defined by Standardised MedDRA Queries (SMQs) or Sponsor Specified Queries (SSQs) as appropriate. The

definition of the SSQs will be maintained in a separate document and will be finalized prior to database lock.

Patient incidence of treatment-emergent ocular AEs of interest will be presented by system organ class, preferred term and maximum severity. Ocular AEs leading to treatment discontinuation will be summarized.

Time to onset and duration to improvement or resolution will be summarized at the patient level for ocular AEs.

Date of onset is defined as the date of earliest occurrence of events of interest. Time to onset for will be summarized by descriptive statistics.

Improvement and resolution of ocular AEs will be derived per patient level. The date of resolution is defined as the earliest time that the patient does not have any ongoing ocular events (i.e. all events with outcome of resolved/recovered or resolved/recovered with sequelae, or all events with severity decreasing to baseline condition or better).

Improvement of ocular AEs is defined based on the worst grade for each patient. If a patient has worst grade 3 or 4 events, date of improvement or resolution is defined as the earliest date that the patient does not have any ongoing grade 3 or 4 events (i.e. the worst grade the patient is experiencing is 2 or below). If a patient has worst grade 2 ocular events of interest, the date of improvement or resolution is defined as the earliest date that the patient does not have any ongoing grade 2 events (i.e. the worst grade the patient is experiencing is 1 or below).

Time to improvement and resolution from first onset and from last treatment of 19A will be summarized for the patients who experienced ocular AEs of interest. Duration of ocular AEs may be summarized by Kaplan-Meier methodology. If a patient does not experience an improvement or resolution, the patient will be censored at last contact date for ocular symptoms, and censored at the date of last ophthalmology exam for corneal findings.

The relationship between ocular AEs and ocular interventions may be explored.

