- AE start date will be imputed as the minimum of (AE condition end date*, last day of the month)
- If the month/year is after the month/year of first dose of investigational agent:
 - AE start date will be imputed as the minimum of (AE condition end date*, last day of the month)

* Only use condition end date if known and complete end date is available.

The following algorithm should be used to impute AE condition end dates. The AE records for a condition/event should be sorted by the imputed start dates then record position (order of entry into the eCRF). After sorting, if any condition end date month/year is greater than any subsequent record end date month/year, then change the imputed start day only to end of month. Repeat as necessary.

After sorting the AE records, apply the following rules to partial or missing AE condition end dates:

For all records excluding the last chronological record for a condition/event

- AE condition end date will be imputed as the start date of the subsequent record

For the last chronological record for a condition/event

- If outcome is “recovered/resolved”, ”recovered/resolved with sequelae”, or “fatal” apply the following:
 - If only year is provided for the end date and year is equal to the year of the last dose date:
 - AE condition end date will be imputed as the minimum of (last dose date+30, death date, data extraction date, December 31st of the end date year)
 - If only year is provided for the end date and year is not equal to the year of the last dose date:
 - AE condition end date will be imputed as the minimum of (death date, data extraction date, December 31st of the end date year)
 - If month and year are provided for the end date:
 - AE condition end date will be imputed as the minimum of (death date, data extraction date, last day of the end date month/year)
- If outcome is “recovering/resolving”, “not recovered/resolved”, “unknown”, or blank:
 - AE condition end date will not be imputed.

Example 1

AESPID 1: Condition/Event HEADACHE

First dose date 01JAN2012

Prior to imputation

Start date	Condition end date	Severity	Outcome	Onset
UNUNK2011	15APR2012	1	not recovered/resolved	pre-ICF
15APR2012	UNMAY2012	2	recovering/resolving	post 1st dose
UNMAY2012	UNJUN2012	1	not recovered/resolved	post 1st dose
UNJUN2012	UNJUN2012	3	recovering/resolving	post 1st dose
UNJUN2012	10JUL2012	2	recovering/resolving	post 1st dose
10JUL2012	--	1	not recovered/resolved	post 1st dose

Post imputation

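### SAP Appendix A's last-dose-plus-30 limit on year-only AE end dates has no floor at the AE start and no exception for fatal or long-followed events, so a few records can get impossible or too-early end dates

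*SAP*

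**What the plan says.** SAP Appendix A sets missing or partial AE end dates. The rule in question is limited in three ways. It applies "For the last chronological record for a condition/event"; the outcome must be recovered, recovered with sequelae, or fatal; and it applies "If only year is provided for the end date and year is equal to the year of the last dose date". The end date is then "imputed as the minimum of (last dose date+30, death date, data extraction date, December 31st of the end date year").

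The two neighbouring rules have no last-dose term. With a year-only end date in a different year, the end is "imputed as the minimum of (death date, data extraction date, December 31st of the end date year"). With month and year known, it is "imputed as the minimum of (death date, data extraction date, last day of the end date month/year"). Records with any other outcome (recovering, not recovered, unknown, blank) get no imputed end date.

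SAP 6.5 uses imputed AE dates for event duration and treatment-emergent status. SAP 7.6.1.1.1 makes recovery of ocular AEs a named output: "Time to improvement and resolution from first onset and from last treatment of 19A will be summarized".

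Follow-up runs past 30 days by design. Protocol 7.7.5 states: "In the event of ocular toxicity, ophthalmology exams should be conducted at least monthly during the follow-up period", until resolution or return to baseline. Protocol 7.7.1.3 adds: "Certain non-serious AEs of interest may be followed until resolution, return to baseline, or study closure". The same section follows SAEs until they resolve or stabilise, and collects treatment-related SAEs that begin after the reporting period.

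**The concern.** A minimum that includes last dose + 30 is a hard ceiling, and no term in the rule refers to the record's own start. The re-sorting step in Appendix A adds no such floor, and neither worked example there reaches this branch. Three things follow from the text:

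- A record that starts after last dose + 30, or whose start is known only to the month and is moved to month-end, can end before it starts.
- A fatal AE can end before the patient's death, although the death date is known.
- An ocular AE followed beyond day 30 enters the time-to-resolution summary as an observed resolution at or before last dose + 30, while a patient with no recorded resolution is censored.

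At stake are the duration and reversibility summaries for ocular AEs, which the SAP singles out as AEs of special importance. No efficacy result is touched. Treatment-emergent status is little affected, because for post-baseline events it rests on onset.

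**Working it through.** The plan gives no figure to reproduce for this branch, so I applied the rule to dated examples. All patient dates are assumptions. Duration is End - Start + 1, from SAP 6.4.

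**Impossible dates** (last dose 1 June 2017, end year 2017, data extraction later)

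- Limit: 1 June + 30 = 1 July 2017.
- Late related SAE starting 10 August: 1 July - 10 August + 1 = -40 + 1 = **-39 days**.
- Fatal AE with death on 20 August: imputed end min(1 July, 20 August, 31 December) = 1 July, which is **50 days before death**.

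**Month-only start** (Cycle 1 Day 1 on 9 January 2017, no delays, Cycle 3 Day 1 on 20 February, end year 2017)

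- Imputed end: 20 February + 30 = 22 March.
- A start known only as March 2017 is imputed to 31 March.
- Duration: 22 March - 31 March + 1 = **-8 days**, even if the true onset was inside the 30 days. If the last dose is taken as the last RICE day (22 February), the end is 24 March and the duration is -6 days.

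**Too-early resolution** (same patient, last dose 20 February)

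| True resolution, days after last dose | Year-only rule | Too short by | Same event, month known |
|---|---|---|---|
| 60 | 30 | 30 | 69 |
| 90 | 30 | 60 | 100 |
| 180 | 30 | 150 | 192 |

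**Too-late resolution** (same patient). An AE starting on Cycle 1 Day 15 (23 January) that truly resolved two weeks later, on 6 February, lasted 15 days. The rule ends it on 22 March and gives 59 days.

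**Jump at the year boundary**

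- Last dose 20 November 2017, end year 2018: 31 December 2018, or 406 days after the last dose.
- Last dose 20 January 2018, end year 2018: 30 days.

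**Effect within affected records, and the obvious alternative.** Assume last-dose dates spread evenly over the year, exponential resolution times after the last dose, and only events that resolve in the same calendar year:

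| Assumed mean (days) | Truly after day 30 | True mean | Mean under rule | Mean under 31 December | Mean absolute error, rule | Mean absolute error, 31 December |
|---|---|---|---|---|---|---|
| 60 | 55% | 48 | 30 | 207 | 33 | 158 |
| 90 | 64% | 63 | 30 | 214 | 45 | 151 |
| 180 | 74% | 87 | 30 | 226 | 65 | 139 |

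The figures are rounded and the exponential means are assumptions. They describe affected records that resolve after the last dose, not the ocular summary as a whole.

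**The case against.** The strongest reply is about reach. The limit bites only when four conditions meet: last record, recovered or fatal outcome, end date known only to the year, and that year equal to the last-dose year. Roughly monthly eye exams make it likely that the month of ocular resolution is known, and that leads to a rule without the limit. Resolution dates are a CRF field, edit checks raise queries, and SAEs are reported within 24 hours and followed. The late-SAE and fatal examples are therefore edge cases that a query should close. This stands: the overall effect is probably small and cannot be sized from the documents.

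The limit also has a basis. Protocol 7.7.1.3 follows ordinary non-serious AEs only to the EOT visit or 30 days after last treatment, whichever is later. This stands for those AEs, but not for ocular AEs and SAEs, which are followed longer.

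A reader might infer three stronger things that the documents do not support:

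- That lasting ocular toxicity in general will look resolved within a month. Unresolved events get no imputed end and are censored, and the month counts from the last dose, not from onset. Appendix A does not say whether the last dose means 19A or any study treatment. If it means any treatment, time from the last 19A dose can be 32 days, or 74 days if 19A was given only in Cycle 1.
- That the error always favours the drug. For an AE that resolved during treatment, the rule lengthens the duration.
- That deleting the limit in favour of 31 December corrects the rule. Under the model above, that date is further from the truth on average. It is a conservative choice, not a more accurate one.

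**Conclusion.** The defect is real and narrow. As written, the rule can produce negative durations (-39 and -8 days in the examples) and a fatal AE that ends before death (50 days in the example). These are wrong at any frequency. For ocular AEs and SAEs followed beyond the reporting period it also conflicts with the trial's own follow-up: a true resolution at day 60, 90 or 180 is recorded as day 30. This assumes that the ocular resolution summary uses the Appendix A end dates, the only end-date convention the SAP gives. The number of affected records is not given and is probably small. The summaries are descriptive, and neither the primary nor the key secondary analyses are involved. It is worth correcting before database lock because the correction is cheap.

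**What to change.** In SAP Appendix A, for the last chronological record:

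1. Add that the imputed end date may not be earlier than the AE start date.
2. Set the end date of a fatal AE to the death date.
3. For ocular AEs of interest and SAEs followed beyond the reporting period, do not apply the last-dose-plus-30 limit. Use the first exam or contact at which the event is recorded as absent. If there is none, treat the end as censored, or as interval-censored within that year.
4. State whether the last dose means 19A or any study treatment.

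Keep the limit for other AEs, subject to items 1 and 2; do not substitute 31 December for all AEs. Reporting the number of records with year-only end dates would show how much this matters.

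The cost is a few lines of SAP text and programming, with no change at sites. The affected ocular records will show slightly longer, less favourable durations.

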Appendix B Definition of the Term “Treatment-Emergent” with Respect to AE Classification

The algorithm below should be used to determine whether an adverse event (AE) is classified as a treatment-emergent adverse event (TEAE). A TEAE is defined as any AE which is newly occurring or worsening in severity, where newly occurring means that the AE was not present at baseline. For ease of reading, both pre-existing conditions and AEs will be referred to as AEs for the remainder of this document. AE dates should be imputed in accordance with the algorithm detailed in Appendix A prior to determination of TEAE classification. Details of the TEAE classification are as follows:

1. Determine the first/earliest dose date of any study treatment (for combination studies this includes any component of the regimen)
2. **Baseline AEs:** classify an AE as a baseline AE if it satisfies both of criteria a and b below:
 - a The onset period field is: “started before the signing of informed consent”; or “started after consent but before the first dose of any study treatment”; or, the onset period field is missing and the AE start date is prior to the first dose date of any study drug (step 1, above).
 - b The stop date satisfies either of i or ii below:
 - i. The stop date is the same as or a later date than the first dose date of any study treatment
 - ii. The stop date is missing with outcome equal to
 - recovering/resolving (this outcome may or may not be associated with a date), or
 - not recovered/not resolved, or
 - unknown.
 - Note: if the AE has no outcome or stop date provided, the CRF data should be queried
 - c Note: If the event ended on Day 1 (the date of first dose of any study drug) it will be considered a baseline event.
3. **Post-baseline AEs:** classify an AE as post-baseline if it meets either of criteria a or b below:
 - a The onset period of the AE is “started after the first dose of any study treatment”
 - b The onset period of the AE is missing and the AE start date is the same as or a later date than the first dose date of any study treatment
4. Compare post-baseline AEs to baseline AEs using the lower level term (LLT) and determine classification. **Note that classification may not be possible and the TEAE variable will be missing:**
 - a Classify all baseline AEs as not treatment emergent (not TEAEs).

- b If a baseline and post-baseline AE have the same LLT but the post-baseline AE has a greater CTC grade then classify the post-baseline AE as a TEAE. If the post-baseline grade is less than or equal to the baseline grade then the post-baseline AE is not a TEAE.
- c If there are no baseline AEs with a matching LLT for the post-baseline AE then classify the post-baseline AE as a TEAE.
- d If the post-baseline AE is uncoded then classify the post-baseline AE as a TEAE.

NOTE:

1. **For summaries which include only treatment emergent AEs include all AEs which are classified as TEAEs as well as those AEs for which TEAE status could not be determined (e.g., the value of the TEAE variable may be missing if the event cannot be identified as baseline or post-baseline - missing information on the AE CRF should be queried). Only exclude those AEs which were determined to not be treatment emergent.**
2. **Events that have an end date prior to the first dose date (e.g. protocol procedure related events) should be classified as not treatment emergent (not TEAEs).**

APPENDIX C: CALCULATION OF VFQ-25 COMPOSITE AND SUBSCALE SCORES

The eleven vision-targeted subscales generated from the VFQ-25 questionnaire and the items included in each subscale are presented in Table 1 and Table 3.

The scoring of VFQ-25 is a two-step process:

First, original numeric values from the survey are re-coded following the scoring rules outlined in Table 2. All items are scored so that a high score represents better functioning. Each item is then converted to a 0 to 100 scale so that the lowest and highest possible scores are set at 0 and 100 points, respectively. In this format scores represent the achieved percentage of the total possible score, e.g. a score of 50 represents 50% of the highest possible score.

In step 2, items within each subscale are averaged together to create the 12 subscale scores. Table 3 indicates which items contribute to each specific sub-scale. Items that are left blank (missing data) are not taken into account when calculating the scale scores. Sub-scales with at least one item answered can be used to generate a subscale score. Hence, scores represent the average for all items in the sub-scale that the respondent answered.

Composite Score Calculation

To calculate an overall composite score for the VFQ-25, simply average the vision-targeted subscale scores, excluding the general health rating question. By averaging the subscale scores rather than the individual items we have given equal weight to each sub-scale, whereas averaging the items would give more weight to scales with more items.

Table 1. VFQ-25 Question Numbers and the Sub-Scales

VFQ-25 Question #	Sub-scale	VFQ-25 Question #	Sub-scale
1	general health	15	Driving (filter item)
2	general vision	15a	Driving (filter item)
3	well-being/distress	15b	Driving (filter item)
4	ocular pain	15c	driving
5	near vision	16	driving
6	near vision	16a	driving
7	near vision	17	role limitations
8	distance vision	18	role limitations
9	distance vision	19	ocular pain
10	peripheral vision	20	dependency
11	social	21	well-being/distress
12	color vision	22	well-being/distress
13	social function	23	dependency
14	distance vision	24	dependency

		25	well-being/distress
--	--	----	---------------------

Table 2. Scoring Key: Recoding of Items

Item Numbers	Change original response category (a)	To recoded value of:
1,3,4,15c(b)	1	100
	2	75
	3	50
	4	25
	5	0
2	1	100
	2	80
	3	60
	4	40
	5	20
	6	0
5,6,7,8,9,10,11,12,13,14,16,16a	1	100
	2	75
	3	50
	4	25
	5	0
	6	*
17,18,19,20,21,22,23,24,25	1	0
	2	25
	3	50
	4	75
	5	100

(a) Precoding response choices as printed in the questionnaire.

(b) Item 15c has four-response levels, but is expanded to a five-levels using item 15b.

Note: If 15b=1, then 15c should be recoded to "0"

If 15b=2, then 15c should be recoded
to missing. If 15b=3, then 15c should
be recoded to missing.

* Response choice "6" indicates that the person does not perform the activity because of non-vision related problems. If this choice is selected, the item is coded as "missing."

Table 3. Step 2: Averaging of Items to Generate VFQ-25 Sub-Scales

Scale	Number of items	Items to be averaged (after recoding per Table 2)
General Health	1	1

General Vision	1	2
Ocular Pain	2	4, 19
Near Activities	3	5, 6, 7
Distance Activities	3	8, 9, 14
Vision Specific:		
Social Functioning	2	11, 13
Mental Health	4	3, 21, 22, 25
Role Difficulties	2	17, 18
Dependency	3	20, 23, 24
Driving	3	15c, 16, 16a
Color Vision	1	12
Peripheral Vision	1	10

Example of scoring subscale “Near Activities”

Items 5, 6, and 7 are used to generate the near activities subscale score (Table 3). Each of the items has 6 response choices. Response choice 6 indicates that the respondent does not perform the activity because of reasons that are unrelated to vision. If a respondent selects this choice, the answer is treated as missing and an average of the remaining items is calculated. Response choice 5 indicates that an activity is so difficult that the participant no longer performs the activity. This extremely poor near vision response choice is recoded to “0” points before taking an average of all three items. To score all items in the same direction, Table 2 shows that responses 1 through 5 for items 5, 6, and 7 should be recoded to values of 100, 75, 50, 25, and 0 respectively. If the respondent is missing one of the items, the person's score will be equal to the average of the two non-missing items. The number with parenthesis below is the item’s response.

Figure 1. Example of VFQ-25 Scoring Algorithm for Near Activities Sub-Scale

5. How much difficulty do you have reading ordinary print in newspapers? Would you say you have:

- No difficulty at all..... 1
- A little difficulty 2
- Moderate difficulty 3
- Extreme difficulty 4
- Stopped doing this because of your eyesight 5
- Stopped doing this for other reasons or not
interested in doing this..... 6

6. How much difficulty do you have doing work or hobbies that require you to see well up close, such as cooking, sewing, fixing . . . ? Would you say you have:

- No difficulty at all..... 1
- A little difficulty 2

Moderate difficulty 3
 Extreme difficulty 4
 Stopped doing this because of your eyesight 5
 Stopped doing this for other reasons or not
 interested in doing this..... 6

7. Because of your eyesight, how much difficulty do you have finding something on a crowded shelf? Would you say you have:

No difficulty at all..... 1
 A little difficulty 2
 Moderate difficulty 3
 Extreme difficulty 4
 Stopped doing this because of your eyesight 5
 Stopped doing this for other reasons or not
 interested in doing this..... 6

Formula:

$$\text{Subscale Score} = \frac{(\text{Sum of score for each item with a non-missing answer})}{\text{Total number of items with non-missing answers}}$$

Example for Near Activities sub-scale:

$$\text{With responses converted:} = \frac{(25 + 100 + 25)}{3} = 50$$

Note: 100 = Best, 0 = Worst possible score.
